4.4 Handling of measurements obtained for early withdrawals

Participants who withdraw early from the study for any reason will be asked to return to the clinic to complete the SFU visit. The SFU procedures performed at this visit are as shown in the Schedule of Activities in the protocol and will be summarized together with all other SFU visit data in the tables.

4.5 Interim analyses and data monitoring

No formal interim analyses are planned during Part A of this study.

The SMC will be established which will comprise key UCB personnel and investigators from participating sites. The SMC will meet after the sentinel participant in each cohort has completed the 16-day DLT Observation Period during Cycle 1 of study treatment. They will review primarily all safety data for this participant, including the individual DLTs (as applicable). Once the last participant in a given cohort has completed the required 28-day DLT Observation Period, a further SMC meeting will be convened to review all safety data (including DLTs) and any available PK, ADA and PD data from all participants in that cohort (and participants in previous cohorts, if applicable). PK, ADA and PD data reported at each SMC will always be based on the previous cohort due to availability and processing time required for these data. The SMC will then decide whether to halt dose escalation, further expand the cohort to gain additional safety data, or determine the next dose level to be evaluated. Further details are included in the SMC Charter and specifications for the data presentations will be included in a separate output specifications document for the SMC reviews.

All data presented to the SMC will be cumulative in order that the members can review and discuss the data in its totality at the end of all completed cohorts, i.e. all safety information beyond Cycle 1 for all previous cohorts will be presented cumulatively for review during each subsequent SMC meeting.

In addition to the planned SMC data review meetings, UCB and the SMC will have the ability to hold/request *ad hoc* meetings should they be deemed necessary (e.g. if safety concerns arise during Part A of the study and/or during other ongoing nonclinical and clinical studies).

4.6 Multicenter studies

Part A of this study is planned to be conducted at 6 study sites in the UK. With the exception of participant disposition, no summaries will be presented by site.

4.7 Multiple comparisons/multiplicity

Not applicable.

4.8 Use of an efficacy subset of participants

The PPS will be used as the primary analysis set for the summaries of the exploratory antitumor activity endpoints in Part A.

4.9 Active-control studies intended to show equivalence

Not applicable.

4.10 Examination of subgroups

Not applicable.

5 STUDY POPULATION CHARACTERISTICS

5.1 Study participant disposition

The number of study participants who were screened for Part A of this study, the number and percentage of screen failures and the primary reasons for screen failure will be summarized for the ES. A listing of participants who did not meet the eligibility criteria for Part A will also be presented for the ES. In addition, the disposition of study participants screened and who received study treatment will be summarized by site. This table will include, for each site and overall, site number, principal investigator name, the dates of the first participant in and the last participant out, the number of participants screened (ES), the number of screen failures, the number of participants who were treated (SS) and included in the PPS, PKS, ADAS and PDS. Disposition in each analysis set across all study sites will be summarized by treatment group.

The number of study participants who received study treatment and the primary reason for discontinuation of study treatment during Part A will be summarized by treatment group, together with the number and percentage of participants who continued participation in the study after discontinuation of study treatment (at subsequent scheduled visits and/or SFU visit and Final Visit). This summary will be based on the SS.

The number of study participants enrolled into Part A, who were screen failures as well as the number of eligible participants who were assigned to a study cohort but not treated will be presented for the ES. For those participants who did not receive study treatment, the reasons for early discontinuation from the study will be summarized.

Of those participants who received study treatment, the number and percentage of participants who completed the study (i.e. participants who received at least 2 complete cycles of study treatment and attended the SFU visit), who received at least 2 complete cycles of study treatment but who did not attend the SFU visit and who discontinued early from Part A, together with the primary reasons for study discontinuation will be presented for all participants.

The number and percentage of participants who discontinued due to AEs will be summarized separately for all participants, based on the SS. This will be used for European Union Drug Regulating Authorities Clinical Trials (EudraCT) reporting.

Visits impacted by COVID-19 will be listed for the ES. This listing will include, visit, visit date, relative day, impact category (e.g. visit performed out of window, visit performed by telephone, visit not done, missed study drug administration/dispensation, termination of study

participation), relationship to COVID-19 (confirmed COVID-19 infection, suspected COVID-19 infection, general circumstances around COVID-19 or other) and a narrative for the event. The number and percentage of participants with visits impacted by COVID-19 will be presented by treatment group and by impact category. This summary will be presented for the different relationships to COVID-19. The denominator for the percentage calculations will be the number of participants in the SS.

In addition, the following listings will be presented:

- Study participant disposition (ES);
- Study treatment discontinuation (SS);
- Study discontinuation (ES);
- Visit dates (ES);
- Participant analysis sets and exclusions from analysis sets (ES)*.

* DES is not included in this listing as it is only relevant for the SMC, and not required for the reporting of data in the CSR.

The listing of study participant disposition will include the date of informed consent, date and time of first and last dose of study treatment, date of early study discontinuation (if applicable) and primary reason for discontinuation. The listing of study treatment discontinuation will include date and time of first and last dose of study treatment, date of decision to discontinue study treatment and primary reason for discontinuation of study treatment, date of clinical progression (if applicable), number of doses of study treatment received (based on 2 doses per cycle), total dose of study treatment received across all cycles, number of complete cycles of study treatment received, and whether or not the participant had continued participation in the study (at subsequent visits, the SFU visit or the Final Visit).

Note that a participant is deemed to have completed a full cycle of study treatment if they received a dose of study treatment on Days 1 and 15 of the cycle and a decision was not made to discontinue their study treatment up to and including Day 28 relative to Day 1 of the cycle. This will be derived based on a participant's last dose of study treatment and whether or not the participant attended the visit at which they were scheduled to receive their next dose of study treatment. For example, if a participant received study treatment on Day 15 of Cycle 1, they attended the clinic on Day 1 of Cycle 2 for their next dose of study treatment then the participant will be counted as having completed Cycle 1. If the participant did not attend Day 1 of a subsequent cycle, then it is likely that a decision was made to discontinue their treatment and/or the study. Therefore, the date that the decision was made to discontinue study treatment will be used to determine whether the participant completed a cycle of study treatment. If a decision was made to discontinue study treatment on >Day 28 relative to Day 1 of the particular cycle then the participant will be counted as having completed the cycle. For any interim deliveries at a data cut-off, if the participant did not attend Day 1 of their next cycle and there was no decision to discontinue study treatment, then the latest date available for that participant should be used to determine whether they have completed a 28-day cycle.

Whether or not a participant has completed the study is defined as having received at least 2 complete cycles of study treatment and attended the SFU visit. The investigator will record a

study participant's disposition status at study termination according to this definition of a 'completed' participant, however, a study completion flag will also be programmatically derived based on the relevant data on the database and the above rules for defining completion of a full cycle of study treatment.

The listing of study discontinuation will include the primary reason for early study discontinuation, the number of cycles of study treatment received, and the total number of days on study treatment.

The total number of days on study treatment will be calculated as follows:

$$\begin{aligned} \text{Total Number of Days on Study Treatment} \\ = (\text{Date of Last Dose Received} - \text{Date of First Dose Received}) + 1 \end{aligned}$$

5.2 Protocol deviations

Important protocol deviations will be identified and classified by the deviation types defined in the IPD specification document, as per [Section 3.4](#).

A listing of all IPDs identified at the DEM will be presented for all study participants based on the SS and will include the deviation type and description. In addition, a listing of all protocol deviations related to COVID-19 (whether considered important or not) will be presented for the SS. The number and percentage of participants in the SS with IPDs will be summarized by treatment group and for all participants for each deviation type. The number and percentage of participants who were excluded from the PPS will also be presented. The denominator for the percentage calculations will be the number of participants in the SS. A summary will also be presented for all protocol deviations related to COVID-19, all IPDs related to COVID-19 and all IPDs related to COVID-19 leading to exclusion from the PPS.

6 DEMOGRAPHICS AND OTHER BASELINE CHARACTERISTICS

6.1 Demographics

A by-participant listing of demographics will be presented based on the ES. This will include the year of birth, age (as entered by investigator in the eCRF in years), sex, race, ethnicity, height (in cm), weight (in kg) and body mass index (BMI, in kg/m²). Height will be the measurement obtained at the Screening visit and weight will be the last non-missing value prior to the first dose of study treatment.

The BMI will be derived in the database using the height and weight measurements recorded at the Screening visit and will be automatically reported to 1 decimal place on the eCRF.

All demographic characteristics (except for date of birth) will be summarized by treatment group and for all study participants based on the SS. The summary of age will include descriptive statistics and categorical summaries, the latter based on requirements for EudraCT and clinicaltrials.gov reporting.

For the EudraCT reporting, the categories will include:

- 18 to <65 years;

- 65 to <85 years.

For clinicaltrials.gov reporting, the categories will include:

- ≤ 18 years;
- 19 to <65 years;
- ≥ 65 years.

Childbearing potential and method of birth control will be listed for the ES.

6.2 Cancer history

All cancer history data for Part A participants will be listed for the ES. This listing will include date of initial diagnosis, tumor type, TNM Classification of Malignant Tumors (TNM) classifications and stage, Duke's score and Gleason score (if relevant to the tumor type), histological and cytological diagnosis details (as relevant), whether the participant had any metastases and associated anatomical location, and whether the participant had received any prior anti-cancer therapies (including the number of lines of any prior systemic therapies, prior radiation therapies and prior anti-cancer surgeries).

Time since initial diagnosis (calculated in months using date of Screening visit and date of initial diagnosis and multiplying the duration in days by 12/365.25), tumor type, T, N, M classifications and TNM stage, Duke's score, Gleason score, presence of metastases and anatomical location of metastases will be summarized by treatment group and for all study participants based on the SS. In the summaries of categorical variables, percentages will be calculated based on the number of study participants with non-missing data. Further, for the cM0(i+) M classification, Duke's score and Gleason score, the denominator for the percentage calculation will be the number of study participants for which these assessments are applicable (since they only apply to certain tumor types).

6.3 Prior anti-cancer therapy

Details recorded for each line of prior anti-cancer systemic therapy received by a study participant will be listed for the ES. This listing will include the line and type of systemic therapy, intent, drug name and dose, formulation, indication (current/ultimate), start and end dates, number of cycles received and the number of days per cycle, the participant's best response and the date of that best response, reason for discontinuation and whether the participant had disease progression prior to the next line of systemic therapy. If there was progression, then the date of progression will also be listed. In addition, time from completion of the last prior anti-cancer systemic therapy to the start of study treatment, whether the participant had progression after the last line of systemic therapy and, if so, the time from progression to the start of study treatment will be derived and listed.

For those participants in the ES who received prior radiotherapy, the following data will be listed: treatment site, type of radiotherapy, intent, settings (concurrent with other anti-cancer systemic therapy or stand-alone radiation therapy), and, if concurrent radiotherapy, the anti-cancer systemic therapy line that the radiotherapy was given with and the drug name. In addition, the start and stop dates, total cumulative dose (if known), number of fractions (if known), the

participant's best response to radiotherapy and whether the tumor at the treatment site had progressed since radiotherapy will be included in this listing.

A further listing of prior anti-cancer radiotherapy with systemic therapy regimens will be presented for participants in the ES who had concurrent prior systemic therapy and radiotherapy as their prior anti-cancer therapy. This listing will include the relevant data described above together with the participant's best response to that regimen.

Date of surgery/procedure, anatomical location, description of the surgical procedure and whether the tumor was completely removed will be listed for those study participants in the ES who had prior anti-cancer surgeries or procedures.

The following summaries of prior anti-cancer therapy regimens and surgeries will be presented by treatment group and for all participants for the SS:

- Number of prior anti-cancer therapy regimens (0, 1, 2, 3, >3) (including all anti-cancer systemic therapy lines given alone and concurrently with radiotherapy)
- Best response to the most recent prior anti-cancer therapy regimen
- Number of prior anti-cancer systemic therapy + radiotherapy regimens (0, 1, 2, 3, >3)
- Best response to the most recent anti-cancer systemic therapy + radiotherapy regimen
- Reasons for discontinuation of the most recent line^[a]
- Time from completion of most recent line^[a] to the start of study treatment (<1 month, 1-<3 months, 3-6 months, >6 months)^[b]
- For participants that progressed after their most recent line^[a], the time from progression to the start of study treatment (<1 month, 1-<3 months, 3-6 months, >6 months)^[b]
- Number of prior anti-cancer radiotherapies (including radiotherapies given alone and concurrently with anti-cancer systemic therapy) (0, 1, 2, >2)
- Number of prior anti-cancer surgeries and procedures (0, 1, 2, >2)

^[a] Most recent line is the last prior anti-cancer therapy regimen received which may be a prior anti-cancer systemic therapy given alone or concurrently with radiotherapy.

^[b] 1 month = 30 days.

Time from completion and time from progression relative to the last line of anti-cancer systemic therapy will also be summarized using frequency counts and percentages as well as summary statistics.

The number and percentage of participants with any prior anti-cancer systemic therapy, and any prior anti-cancer systemic therapy given concurrently with radiotherapy will be summarized for the SS by treatment group and for all participants, and by WHODD Anatomical Main Group [Level 1 term text], Pharmacological Subgroup [Level 3 term text] and PT.

6.4 Cancer status at Screening

The current cancer status of study participants at entry into Part A of this study will be assessed at the Screening visit and listed for the ES. This listing will include tumor type, T, N and M classifications and TNM stage, Duke's score and Gleason score (if relevant to the tumor type),

histological and cytological diagnosis details (as relevant), whether the participant has any metastases and associated anatomical location, whether the tumor is recurrent and whether the participant had relapsed from their last line of anti-cancer therapy.

Tumor type, TNM classifications and stage, Duke's score, Gleason score, presence of metastases and anatomical location of metastases, and time since relapse on last line of therapy (calculated in days using the date of the Screening visit and date of relapse) will be summarized by treatment group and for all study participants based on the SS. In the summaries of categorical variables, percentages will be calculated based on the number of study participants with non-missing data. Further, for the cM0(i+) M classification, Duke's score and Gleason score, the denominator for the percentage calculation will be the number of study participants for which these assessments are applicable (since they only apply to certain tumor types).

6.5 Medical history and concomitant diseases

Medical history will be listed for the ES and summarized by MedDRA system organ class (SOC) and preferred term (PT) by treatment group and for all study participants for the SS. The reported term will be included in the listing. Previous medical history (any previous medical conditions with a stop date prior to the start of study treatment) and ongoing medical history (any ongoing medical conditions with a missing stop date but recorded as ongoing on the eCRF) will be summarized separately. These summaries will include the number and percentage of study participants and will be sorted alphabetically by SOC and by descending incidence of PT within each SOC, based on the incidence in all study participants.

Non-anti-cancer procedure history will be listed for the ES and concomitant medical procedures performed during the study will be listed for the SS.

6.6 Prior and concomitant medications

Prior medications will include any medications that started prior to the date of the first dose of study treatment. This will include medications that started prior to the first dose and continued after.

Concomitant medications will include medications with a start date on or after the first dose of study treatment and prior to the date of the last dose of study treatment + 30 days, and whose stop date is either missing, or on or after the date of the first dose of study treatment. Any medications with a start date prior to the first dose of study treatment and a stop date after, or continued to be ongoing during the study, will also be classified as concomitant medications. Medications with a start date > 30 days after the last dose of study treatment will be considered as post-study medications and will not be included in the summaries of concomitant medication.

Any medication that started prior to, and stopped after the first dose of study treatment, or continued to be ongoing during the study, will be classified as both prior and concomitant.

Any medications with missing start dates will be classified as both prior and concomitant provided that a stop date is not present or a stop date is present and it is prior to the first dose of UCB6114.

Any medications with partially missing dates will be handled as described in [Section 4.2.3](#) to classify them as prior or concomitant.

All medications (prior, concomitant and post-study) will be listed for the ES. Any prohibited concomitant medications, rescue medications or steroid use will be identified via a medical review and flagged in this listing.

Prior and concomitant medications (per the definitions above) will be summarized for the SS by treatment group and by WHO-DD Anatomical Main Group [Level 1 term text], Pharmacological Subgroup [Level 3 term text] and PT. The reported term will be included in the listing. Separate summaries will be presented for prior medications and concomitant medications. As per the definitions above, prior medications which continued into the Treatment Period will also be classified as concomitant and will be included in both summaries.

All tabulations will be sorted alphabetically by Level 1 term, alphabetical Level 3 term within Level 1 and decreasing frequency of PT in all study participants.

A glossary of all prior and concomitant medications will be presented for the SS including the Anatomical Main Group (Level 1), Pharmacological Subgroup (Level 3), PT and reported term.

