be regarded as treatment-emergent. For medications, the medication will be classified as concomitant.

- If the onset/start date is completely missing then the onset/start date will be imputed to the date of first dose of study treatment and therefore, for AEs, the event will be regarded as treatment-emergent and, for medications, the medication will be classified as concomitant.

The following rules will be applied to partial end/stop dates:

- If only the month and year are specified, then the last day of the month will be used;
- If only the year is specified, then December 31 of the known year will be used;
- If the stop date is completely unknown, the stop date will not be imputed.

Note that the start date or stop date of a prior medication (partial or otherwise) should not be imputed past the Screening date - 1.

In addition to onset and stop dates, the onset and end times of AEs occurring on the day of infusion will be collected on the eCRF. Onset and end times may also be recorded for other AEs that do not occur on the same day as the infusion. The duration of AEs with onset and end times will be calculated in days and hours:minutes (hh:mm) as:

$$\text{Duration of AE} = \text{End Date and Time} - \text{Onset date and time}$$

In cases where only the onset and stop dates are recorded for an AE, the duration of an AE will be calculated in days as:

$$\text{Duration of AE} = (\text{Stop Date} - \text{Onset Date}) + 1$$

Note that for participants who have an AE which starts and stops on the same day, but with only a start time or only a stop time recorded, it will be assumed that their AE started from 00:00 (if no start time is recorded) and ended at 23:59 (if no stop time is recorded) on that day.

If the date of a participant's initial diagnosis is incomplete, it will be imputed to the most recent feasible date for the calculation of time since initial diagnosis as follows:

- If only the day is missing, it will be imputed to the last day of the known month;
- If the day and month are missing, it will be imputed to December 31 in the known year;
- If the date of initial diagnosis is completely missing, then time since initial diagnosis will not be calculated.

The above date imputation rules will be applied to partially missing stop dates of a participant's last prior anti-cancer systemic therapy as well as partially and completely missing dates of progression/relapse on last prior anti-cancer systemic therapy.

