6.6 Prior and concomitant medications

Prior medications will include any medications that started prior to the date of the first dose of UCB6114. This will include medications that started prior to the first dose of UCB6114 and continued after.

Concomitant medications will include medications with a start date on or after the first dose of UCB6114 and prior to the date of the last dose of UCB6114 + 30 days, and whose stop date is either missing, or on or after the date of the first dose of UCB6114. Any medications with a start date prior to the first dose of UCB6114 and a stop date after, or continued to be ongoing during the study, will also be classified as concomitant medications. Medications with a start date > 30 days after the last dose of UCB6114 will be considered as post-study medications and will not be included in the summaries of concomitant medication.

Any medication that started prior to and stopped after the first dose of UCB6114 or continued to be ongoing during the study, will be classified as both prior and concomitant.

Any medications with completely missing start dates will be classified as both prior and concomitant provided that a stop date is not present or a stop date is present but is prior to the first dose of UCB6114.

Any medications with partially missing dates will be handled as described in [Section 4.4.1](#) to classify them as prior or concomitant.

All medications (prior, concomitant and post-study) will be listed for the ES. Any prohibited concomitant medications, rescue medications or steroid use will be identified via a medical review and flagged in this listing.

Prior and concomitant medications (per the definitions above) will be summarized for the SS by treatment group and by WHODD Anatomical Main Group [Level 1 term text], Pharmacological Subgroup [Level 3 term text] and PT. The reported term will be included in the listing. Separate summaries will be presented for prior medications and concomitant medications.

All tabulations will be sorted alphabetically by Level 1 term, alphabetical Level 3 term within Level 1 and decreasing frequency of PT in all study participants.

A glossary of all prior and concomitant medications will be presented for the SS including the Anatomical Main Group (Level 1), Pharmacological Subgroup (Level 3), PT and reported term.

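### Section 6.6 of both SAPs classes a medication with a missing start date that stopped before first dose as concomitant, contradicting its own definition and fitting poorly with the date-imputation rules

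*SAP*

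**What the plan says.** The Part A SAP, Section 6.6, defines prior medication by start date alone: "Prior medications will include any medications that started prior to the date of the first dose of study treatment". It gives two routes to concomitant:

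- A medication starting on or after first dose, within a limit set by the last dose, is concomitant if it is one "whose stop date is either missing, or on or after the date of the first dose of study treatment".
- A medication starting before first dose is concomitant if its use ran past first dose or was ongoing. Such a medication counts in both classes: "Any medication that started prior to, and stopped after the first dose of study treatment, or continued to be ongoing during the study".

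A separate sentence covers unknown start dates: "Any medications with missing start dates will be classified as both prior and concomitant". It attaches this condition: "provided that a stop date is not present or a stop date is present and it is prior to the first dose of UCB6114". The next sentence sends only partially missing dates to Section 4.2.3, so this one concerns completely missing start dates. Section 6.6 of the Part A1 SAP says so outright and keeps the condition: "provided that a stop date is not present or a stop date is present but is prior to the first dose of UCB6114".

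Section 4.2.3 of the Part A SAP has its own bullet for the same situation: "If the onset/start date is completely missing then the onset/start date will be imputed to the date of first dose of study treatment". The bullet then classes the medication as concomitant. It does not mention prior and makes no exception for a stop date before first dose. Section 4.4.1 of the Part A1 SAP has the same bullet.

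**The concern.** A medication that ended before first dose was not taken alongside study treatment. It meets neither route to concomitant in Section 6.6, yet the missing-start sentence puts it there. The known-stop case in which concomitant use is plausible, a stop on or after first dose, is left out of the sentence.

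A programmer also has two rules for completely missing start dates, in 6.6 and in the imputation section, with different results and no order of precedence. At stake is whether the prior and concomitant medication tables contain the records that their definitions say they contain.

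**Working it through.** No stated figure is involved, so the check is a case-by-case reading. Take a medication with a completely missing start date and vary the stop date. Each case is classified by three texts: the 6.6 missing-start sentence, the 6.6 general definitions, and the 4.2.3/4.4.1 bullet.

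| Stop date | 6.6 missing-start sentence | 6.6 general definitions | 4.2.3 / 4.4.1 bullet |
|---|---|---|---|
| Absent | Both | Both, if the start is taken to precede first dose | Concomitant only |
| Before first dose | Both | Prior only | Concomitant, with imputed start later than stop |
| On or after first dose | No classification | Concomitant, possibly also prior | Concomitant only |

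**Stop absent.** The 6.6 sentence agrees with the definitions if the start is taken to precede first dose. The imputation bullet disagrees, because it gives concomitant alone.

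**Stop before first dose.** The start must precede the stop, so it precedes first dose and the medication is prior. Neither route to concomitant is open: the first needs a stop that is missing or not earlier than first dose, the second needs use that continued past first dose. The 6.6 sentence nevertheless gives both classes. The imputation bullet does not repair this, since it places the start on the date of first dose, after the known stop. The partial-date bullets in the same section check for an imputed start that falls after the end date. The completely-missing bullet has no such check.

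**Stop on or after first dose.** The 6.6 sentence gives nothing. The imputation bullet gives concomitant, so the record still reaches the concomitant table. Whether it also belongs in the prior table is unsettled.

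**A further clash.** The imputation section also says that a prior medication's dates are not to be imputed beyond the day before Screening. Imputing to first dose breaks that limit for every record that 6.6 also calls prior.

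**Size in a table.** The number of affected records is not given. For illustration, one wrongly counted participant adds 1/3 = 33.3, 1/6 = 16.7 or 1/8 = 12.5 percentage points to a row for a treatment group of 3, 6 or 8. These sizes come from the planned Part A cohorts of 3 to 6 evaluable participants and the Part A1 cohorts of up to 8. The shift occurs only if that participant is not already counted in the row.

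**After the correction.** With the wording proposed below, the three cases become both, prior only and both, consistent with the 6.6 definitions if an unknown start is taken to precede first dose. One boundary remains: for a medication started earlier, the definitions ask for a stop after first dose, whereas for one started on or after first dose they accept a stop on that day. The proposed wording counts a stop on that day as concomitant.

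**The case against.** The strongest reply is that this is a drafting slip with little reach, and much of that stands.

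- **A reader might infer that the rule is wholly reversed and that a missing start with a later stop is uncovered.** The documents do not support this. Sections 4.2.3 and 4.4.1 class that case as concomitant, and the limb of the 6.6 sentence for an absent stop date gives the result that the correction keeps.
- **A reader might infer that every record with an unknown start and a known stop is misclassified.** It is not. Only the records with a stop before first dose are wrongly called concomitant.
- **A reader might infer an effect on PPS membership or PFS censoring.** The text shows none. All medications are listed whatever their derived class, and prohibited medication, rescue medication and steroid use are flagged in that listing by medical review. PPS exclusions are decided at the data evaluation meetings from important protocol deviations. PFS censoring depends on anti-cancer therapy started during the study, found by medical review and from start dates on the survival follow-up pages. A drug that ended before first dose cannot be such therapy.
- **The scope is narrow.** Partially missing start dates follow other rules, which guard against a start after the stop. Prior anti-cancer systemic therapy has its own date handling.

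The reply does not remove the contradiction within Section 6.6 or the conflict with the imputation bullet. Both SAPs carry both problems, with the sentence slightly reworded in Part A1, so this is not an extraction fault.

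**Conclusion.** The point holds in a limited form. In both SAPs, Section 6.6 calls a medication concomitant when its start is completely missing and it is known to have stopped before first dose, against the section's own definitions. The same sentence omits a stop on or after first dose, and the imputation section handles completely missing starts differently.

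If the sentence is programmed as written, every record of the first kind enters the concomitant tables wrongly. How many such records exist is unknown, possibly none. The conclusion assumes that the missing-start sentence in Part A means completely missing, which the sentence after it and the Part A1 wording both support. The demonstrated effect is on descriptive prior and concomitant medication tables only.

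**What to change.** In Section 6.6 of both SAPs, replace the missing-start sentence with two statements:

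- Completely missing start and a stop before first dose: prior only.
- Completely missing start and a stop that is missing, or on or after first dose: both prior and concomitant.

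In the completely-missing-start bullet of Section 4.2.3 (Part A) and Section 4.4.1 (Part A1), add an exception for medications with a stop date before first dose and give the same classification as 6.6. State the class directly rather than deriving it from the imputed date: a start imputed to first dose fails the definition of prior and crosses the limit on imputing prior medication dates. The adverse-event part of the bullet need not change for this point.

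The cost is one sentence and one bullet in each SAP, with a matching change to the derivation of the prior and concomitant flags. No new data are needed.
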